4. SUBJECT SELECTION

4.1 NUMBER OF SUBJECTS

This study will enroll 60 subjects for participation. There are no other sites for this study.

The sample size was chosen to be a sufficient number to assess the effect of Treximet on the WPAI using a crossover design in which patients will serve as their own controls.

Based on previous GSK studies on Treximet utilizing the WPAI, the effect size between Treximet and usual triptan care is expected to be small. In those studies, comparisons of Treximet to placebo yielded differences of 0.4 to 1.4. For this study, a one-point WPAI difference between Treximet and triptan is assumed to be clinically meaningful. Furthermore, the GSK Treximet studies were parallel designs with standard deviations ranging from 2.5 to 3.5. To account for the correlation from patients acting as their own controls in this crossover design, a standard deviation of the difference equal to 2.5 is assumed. Under these assumptions, a total sample of 60, with 30 in each sequence, would power the study at 86%.

4.2 INCLUSION CRITERIA:

A subject will be eligible to participate in this study if all of the following criteria apply:

1. subject is 18 years or older at screening
2. subject has a history of migraine greater than 1 year
3. subject has been diagnosed with migraine before age 50
4. subject is an employed person (is paid wages for his/her work)

5. subject has diagnosis of episodic migraine, by IHS criteria
6. subject uses triptan monotherapy as the primary migraine abortive treatment
7. subject is not pregnant or nursing

4.3 EXCLUSION CRITERIA:

A subject will not be eligible to participate in this study if any of the following criteria apply:

1. subject is less than 18 years of age at screening
2. subject does not have history of migraine greater than 1 year
3. subject was diagnosed with migraine after age 50
4. subject is not currently employed
5. subject does not have diagnosis of episodic migraine
6. subject does not use triptan monotherapy as primary migraine abortive treatment
7. subject is pregnant or nursing
8. subjects with a history of stroke, myocardial infarction (including vasospastic coronary artery disease [CAD] or cardiovascular thrombotic events)
9. subjects with gastrointestinal disease history to include ulcers, bleeding or perforations of the stomach or intestines
10. subjects with a history of significant renal or hepatic disease.

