6 STUDY ASSESSMENTS

The Study Flowsheet (time and events table) provided below lists the study activities throughout the protocol.

STUDY FLOW CHART			
		Washo	

	Screen (Office Visit)	First Arm (Treximet™ or Usual Triptan) - Treat 3 Migraines			ut Windo w (at least 48h post V4 tx) (Office Visit)	Second Arm (Treximet™ or Usual Triptan) - Treat 3 Migraines			EOS (Office Visit)
Procedure	Visit 1	Visit 2	Visit 3	Visit 4	Visit 5	Visit 6	Visit 7	Visit 8	Visit 9
Informed Consent	X								
Inclusion/Exclusion	X								
Office Visit (PE, Vitals Neuro Exam)	X								X
Urine Pregnancy Test (if female and childbearing potential)	X				X				X
Conmeds	X				X				X
AE/SAE collect					X				X
Migraine History & update	X				X				
Medical History- & update	X				X				X
Educ/Disp/Revu Diary	X	X	X	X	Collect	x	x	x	Collect
Randomization	X				Switch TX Arm				
Disp/Take/Collect Study Drug	X	X	X	X	Collect	X	X	X	Collect
WPAI		X	X	X	Collect	X	X	X	Collect
CORS 1				X	Collect			X	Collect
CORS 2								X	Collect
MigraineAct	X			X	Collect			X	Collect
KP Data	X				X				X

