For the secondary outcome Migraine-ACT, a binary outcome will be calculated (e.g. 0=if Migraine-ACT is not favorable, 1=if Migraine-ACT is favorable) and used to identify carryover. [Note: A favorable response in Migraine-ACT is a value of 3 or 4.] The odds of a favorable triptan f/b Treximet sequence will be compared to the odds of a favorable Treximet f/b triptan sequence through an odds ratio, which will be evaluated with a chi-square test (see Toutenburg¹ p. 369). If no significance is found, then the assumption will be that there is no carryover effect. That assumption will be applied when analyzing both the binary and ordinal (levels > 2) values of Migraine-ACT. Treatment differences will be evaluated through a generalized estimating equation with a logit link function (or cumulative logit link function). The models will include trial period, sequence, and treatment as fixed effects. If carryover does exist, then only first trial period results will be used. In that case, treatment differences will be evaluated through a chi-squared test for binary outcomes and through a Mann-Whitney U-test for ordinal outcomes (levels > 2).

All tests for significance will be conducted at the 95% confidence level (i.e. $\alpha = .05$). Analysis will be conducted in SAS® v9.2.

CORS data will be tabulated as follows: For CORS part 1, a frequency count and percent by question answer will be provided. This will be reported by treatment (Treximet™ vs triptan) within period and in total. For CORS part 2, a frequency count and percent will be provided by answer for each question. In addition, a de-identified data set containing CORS information will be provided to Pernix Therapeutics for additional psychometric analysis.

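### The Visit 1 Migraine-ACT score is collected but not used in the section 8.2 carry-over check or first-period fallback, which gives up some precision on a secondary outcome

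*Combined protocol and SAP*

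**What the plan says.** **Collection.** The Migraine-ACT row of the Study Flow Chart (section 6) reads "MigraineAct X X Collect X Collect". The first mark is Visit 1, the screening visit. The other two are Visits 4 and 8, after the third treated attack in each period. The narrative in section 3.1 mentions only the two later completions.

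**Who completes it at Visit 1.** Section 4.2 requires triptan monotherapy as the main abortive treatment, and the questionnaire (Appendix 11.4) asks about the patient's own treatment.

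**Analysis (section 8.2).** A score of 3 or 4 is favorable. Carry-over is judged by an odds ratio between the two sequences, with a chi-square test. If that test is not significant, a GEE follows: "The models will include trial period, sequence, and treatment as fixed effects". If it is significant, only period 1 is used and "treatment differences will be evaluated through a chi-squared test for binary outcomes and through a Mann-Whitney U-test for ordinal outcomes". The Visit 1 score appears in none of these steps.

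**Size.** Section 4.1 states that "a total sample of 60, with 30 in each sequence, would power the study at 86" per cent, for WPAI. No power is given for Migraine-ACT.

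**The concern.** The crossover draws its precision from patients acting as their own controls. The carry-over check and the period-1 fallback both give that up and compare different patients. A baseline on the same instrument helps most in such comparisons, and here it is already on the visit schedule with no stated use.

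Migraine-ACT answers Aim 3. The carry-over check always runs and decides which analysis answers that aim. Carry-over is plausible for this outcome: treatment is open label, and items on comfort and consistency may be rated differently once the alternative has been tried. A 48-hour washout is not designed to remove that. A noisier check is less able to see such a shift, and a noisier fallback is less able to see a treatment difference.

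**Working it through.** **1. The plan's own figure.** Inputs from section 4.1: "a one-point WPAI difference between Treximet and triptan is assumed to be clinically meaningful"; "a standard deviation of the difference equal to 2.5 is assumed"; 60 patients. Section 8.2 adds "All tests for significance will be conducted at the 95% confidence level", taken as two-sided 0.05. Noncentrality = 1/(2.5/√60) = 3.10. The t-test gives 86.2% (df 59) or 86.1% (df 58), and the normal approximation gives 87.3%. The stated 86% is reproduced. The randomization table (Appendix 11.7) counts to 30 and 30.

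**2. What a between-patient comparison costs.** Section 4.1 says "the GSK Treximet studies were parallel designs with standard deviations ranging from 2.5 to 3.5". The same one-point difference at 30 v 30 in period 1 alone, by normal approximation, has power Φ(1/(SD·√(2/30)) − 1.96): 34% at SD 2.5, 25% at 3.0 and 20% at 3.5. This is WPAI, used only to show the scale of the loss.

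**3. Variance algebra for Migraine-ACT.** Let r be the correlation between any two of the Visit 1, period 1 and period 2 scores. The documents give no r, so 0.3, 0.5 and 0.7 are assumptions.
- Period 1: residual variance is multiplied by 1 − r², so effective n per group is 30/(1 − r²) = 33, 40 and 59.
- Sum of the two periods: the share of variance explained by baseline is 2r²/(1 + r) = 14%, 33% and 58%.

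This algebra is for continuous scores. The planned Migraine-ACT tests are binary or ordinal, so it only bounds what to expect.

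**4. Simulated power of the fallback.** Latent normal score cut to 0–4, favorable = 3 or 4, 30 v 30, latent shift 0.5 SD:

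| Latent correlation | Chi-square | Logistic + Visit 1 | Gain | Mann-Whitney | Linear model + Visit 1 | Gain |
|---|---|---|---|---|---|---|
| 0.3 | 34% | 35% | 1 | 44% | 44% | 0 |
| 0.5 | 32% | 37% | 5 | 41% | 50% | 9 |
| 0.7 | 34% | 48% | 14 | 42% | 64% | 22 |

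The linear model stands in for ordinal logistic regression. Taken alone, each test has type I error of about 4–6%. The figures are good to a few points.

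A larger effect (50% v 75% favorable, latent shift 0.674) gives the same pattern. Chi-square against adjusted logistic is 51 v 54%, 53 v 61% and 54 v 71%. Mann-Whitney against the adjusted linear model is 63 v 67%, 66 v 75% and 66 v 87%. Applying the effective n of step 3 to this binary case would give 56, 64 and 81%, from 52% unadjusted, so the algebra overstates what logistic adjustment delivers.

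**5. Carry-over check.** As a stand-in for the planned binary test, take the two-period sum, with a between-sequence difference of 0.8 in units of the single-score SD. Power = Φ(0.8/(s·√(2/30)) − 1.96), where s² = 2(1 + r) unadjusted and 2(1 + r)(1 − 2r²/(1 + r)) adjusted. Unadjusted against adjusted: 49 v 54%, 43 v 59% and 39 v 73% at r = 0.3, 0.5 and 0.7.

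**6. Error rate of the whole procedure.** The fallback runs only after a significant carry-over test, and the period-1 score is part of what that test examined. With no treatment effect and no carry-over (20,000 runs, t-tests and ANCOVA on sums and on period 1 as stand-ins), the period-1 test rejects in 41, 49 and 61% of triggered cases unadjusted, and in 40, 47 and 48% adjusted, at latent correlations of 0.3, 0.5 and 0.7.

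**The case against.** The case against has real force.

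- **It is an efficiency preference.** Chi-square and Mann-Whitney tests are valid for two randomized groups. A chance imbalance at baseline is already allowed for in their error rate, so a reader should not infer that the unadjusted tests are biased. This stands.
- **The reach is limited.** Migraine-ACT is secondary, and with no carry-over the fallback runs about 5% of the time. The GEE also omits the Visit 1 score, but its treatment comparison is within patients and has less to gain. This stands.
- **The correlation may be low.** The Visit 1 answer reflects usual use, not three study-treated work-day attacks, and half the patients are on Treximet in period 1. At 0.3 the gain is negligible. This stands as a limit on size.
- **The Visit 1 score may not be a clean baseline.** A reader might infer that it precedes any Treximet exposure and knowledge of the assignment. Neither is written. Section 4.3 does not exclude earlier Treximet use, and open-label randomization is at the same visit with no stated order. That it rates the usual triptan is itself an inference from the entry criterion and the visit order, though the natural one.
- **A tempting stronger reading is that adjustment makes the carry-over decision safe, or holds the procedure at 5%.** Steps 5 and 6 show otherwise. Even adjusted, power to see an assumed difference of 0.8 is 54 to 73%, and the conditional rejection rate remains far above 5%. The 4–6% applies only to each test taken alone.

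None of this gives a reason to leave a scheduled baseline unused in the two comparisons where it can help.

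**Conclusion.** The point holds as one of precision. Section 8.2 bases the Migraine-ACT carry-over check and the period-1 fallback on unadjusted comparisons, at most 30 against 30 as planned, although a Visit 1 score is on the schedule. No dropout allowance is stated, and a favorable sequence is not defined, so the carry-over test may use fewer patients.

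For any positive baseline correlation, adjustment is expected to help or at worst do little. The size runs from nothing useful at 0.3 to a material gain at 0.7, on the assumed 0.5 SD latent shift and a correlation the documents do not supply. The documents do not support a claim that Aim 3 will be answered wrongly, or that adjustment repairs the rule of testing for carry-over and then choosing the analysis.

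**What to change.** In section 8.2:

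1. Pre-specify the Visit 1 Migraine-ACT score as a covariate in the between-sequence carry-over comparison, for example a logistic model on sequence plus the Visit 1 score. Define the favorable sequence outcome it models.
2. In the first-period fallback, replace the chi-square and Mann-Whitney tests with binary and ordinal logistic regression on treatment plus the Visit 1 score.
3. State in section 6 or 8.2 that the Visit 1 questionnaire is completed before the assignment is known.
4. For the Treximet-first sequence, tabulate the Visit 1 triptan rating beside the later triptan rating. This is descriptive, but it shows directly any shift in how the triptan is rated after Treximet.
5. Say that a non-significant carry-over test is not evidence that carry-over is absent.

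The cost is wording and one model term, with no new data collection. There are two small downsides. The adjusted odds ratio is conditional on baseline, so it does not estimate the same quantity as the unadjusted one. Five ordered levels with 30 per group may leave sparse cells, so the plan should name a rule for merging levels.

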9 STUDY CONDUCT CONSIDERATIONS

The clinical research will be performed according to current Cleveland Clinic IRB Policy regarding Good Clinical Practices. The study principal investigator will oversee the performance of this study and is up to date and certified with CITI.

APPENDIX II.I

PRODUCTIVITY QUESTIONNAIRE

Study ID # _____

Date Completed ____/____/____

Answer the following questions at bedtime of the day you treated your migraine attack with study medication.

Were you scheduled to do paid work during this migraine attack? [Y] Yes [N] No

If Yes, record the number of hours (to the nearest one-half hour) you were scheduled to do paid work during this migraine attack: _____. ____ Hours

Record details of how this migraine attack affected your work and non-work related activities in the table below:

Activity	Number of hours missed from doing activity due to migraine symptoms Zero = 00.0	Number of hours continued to do activity with migraine symptoms Nine hours = 9.0	Estimate how effective you were, compared to your usual performance, while you continued to do activity with migraine symptoms If number of hours doing activity is 00.0, DO NOT COMPLETE. 100% = effective as usual (%)
1. Paid work activities. Complete this row only if you were scheduled to do paid work during this attack.			
2. Activities outside your paid work. (eg, leisure activities, household chores/tasks, family/social activities, etc.)			

APPENDIX II.2

CORS 1

CORS Version 1.0

Page 1

**Completeness of Response Survey
(CORS)**

Please think about your overall experience with your current migraine treatment and check one box for each question below.

1a. How often does one dose of your current migraine treatment completely relieve your headache pain?

None or almost none of the time → **SKIP TO QUESTION 2A.**
 Some of the time
 About half of the time
 Most of the time
 All or almost all of the time

1b. How quickly does your current migraine treatment completely relieve your headache pain?

Less than 30 minutes
 30 minutes to 1 hour
 1 hour to 2 hours
 More than 2 hours

2a. When you have a migraine, how often do you experience neck/shoulder pain?

None or almost none of the time → **SKIP TO QUESTION 3A.**
 Some of the time
 About half of the time
 Most of the time
 All or almost all of the time

2b. How often does one dose of your current migraine treatment completely relieve your neck/shoulder pain when you experience neck/shoulder pain with a migraine?

None or almost none of the time → **SKIP TO QUESTION 3A.**
 Some of the time
 About half of the time
 Most of the time
 All or almost all of the time

2c. How quickly does your current migraine treatment completely relieve your neck/shoulder pain?

Less than 30 minutes
 30 minutes to 1 hour
 1 hour to 2 hours
 More than 2 hours

APPENDIX II.3

CORS 2

APPENDIX II.4

MIGRAINE-ACT

Migraine-ACT		
Question	Yes	No
When you take your treatment: Does your migraine medication work consistently, in the majority of your attacks?		
When you take your treatment: Does the headache pain disappear within two hours?		
When you take your treatment: Are you able to function normally within two hours?		
When you take your treatment: Are you comfortable enough with your medication to be able to plan your daily activities?		
Migraine-ACT Score		

APPENDIX II.5

STUDY DIARY

WEEK 1	WEEK 2
Date: ____ / ____ / ____ Day M T W TH F S SU (please circle one) Headache today Y or N (please circle one) If YES: Time Headache Started: _____ AM/PM Time Headache Stopped: _____ AM/PM Pain Level at Dose Time = _____ Scale of 0 to 10 (with 0 being absence of pain and 10 being worst possible pain)	Date: ____ / ____ / ____ Day M T W TH F S SU (please circle one) Headache today Y or N (please circle one) If YES: Time Headache Started: _____ AM/PM Time Headache Stopped: _____ AM/PM Pain Level at Dose Time = _____ Scale of 0 to 10 (with 0 being absence of pain and 10 being worst possible pain)
Date: ____ / ____ / ____ Day M T W TH F S SU (please circle one) Headache today Y or N (please circle one) If YES: Time Headache Started: _____ AM/PM Time Headache Stopped: _____ AM/PM Pain Level at Dose Time = _____ Scale of 0 to 10 (with 0 being absence of pain and 10 being worst possible pain)	Date: ____ / ____ / ____ Day M T W TH F S SU (please circle one) Headache today Y or N (please circle one) If YES: Time Headache Started: _____ AM/PM Time Headache Stopped: _____ AM/PM Pain Level at Dose Time = _____ Scale of 0 to 10 (with 0 being absence of pain and 10 being worst possible pain)
Date: ____ / ____ / ____ Day M T W TH F S SU (please circle one) Headache today Y or N (please circle one) If YES: Time Headache Started: _____ AM/PM Time Headache Stopped: _____ AM/PM Pain Level at Dose Time = _____ Scale of 0 to 10 (with 0 being absence of pain and 10 being worst possible pain)	Date: ____ / ____ / ____ Day M T W TH F S SU (please circle one) Headache today Y or N (please circle one) If YES: Time Headache Started: _____ AM/PM Time Headache Stopped: _____ AM/PM Pain Level at Dose Time = _____ Scale of 0 to 10 (with 0 being absence of pain and 10 being worst possible pain)
Date: ____ / ____ / ____ Day M T W TH F S SU (please circle one) Headache today Y or N (please circle one) If YES: Time Headache Started: _____ AM/PM Time Headache Stopped: _____ AM/PM Pain Level at Dose Time = _____ Scale of 0 to 10 (with 0 being absence of pain and 10 being worst possible pain)	Date: ____ / ____ / ____ Day M T W TH F S SU (please circle one) Headache today Y or N (please circle one) If YES: Time Headache Started: _____ AM/PM Time Headache Stopped: _____ AM/PM Pain Level at Dose Time = _____ Scale of 0 to 10 (with 0 being absence of pain and 10 being worst possible pain)
Date: ____ / ____ / ____ Day M T W TH F S SU (please circle one) Headache today Y or N (please circle one) If YES: Time Headache Started: _____ AM/PM Time Headache Stopped: _____ AM/PM Pain Level at Dose Time = _____ Scale of 0 to 10 (with 0 being absence of pain and 10 being worst possible pain)	Date: ____ / ____ / ____ Day M T W TH F S SU (please circle one) Headache today Y or N (please circle one) If YES: Time Headache Started: _____ AM/PM Time Headache Stopped: _____ AM/PM Pain Level at Dose Time = _____ Scale of 0 to 10 (with 0 being absence of pain and 10 being worst possible pain)
Date: ____ / ____ / ____ Day M T W TH F S SU (please circle one)	Date: ____ / ____ / ____ Day M T W TH F S SU (please circle one)

Headache today Y or N (please circle one)
 
If YES:
 
Time Headache Started: _____ AM/PM
 
Time Headache Stopped: _____ AM/PM
 
Pain Level at Dose Time = _____ Scale of 0 to 10 (with 0 being absence of pain and 10 being worst possible pain)
	
Headache today Y or N (please circle one)
 
If YES:
 
Time Headache Started: _____ AM/PM
 
Time Headache Stopped: _____ AM/PM
 
Pain Level at Dose Time = _____ Scale of 0 to 10 (with 0 being absence of pain and 10 being worst possible pain)

Date: ____/____/____
 
Day M T W TH F S SU (please circle one)
 
Headache today Y or N (please circle one)
 
If YES:
 
Time Headache Started: _____ AM/PM
 
Time Headache Stopped: _____ AM/PM
 
Pain Level at Dose Time = _____ Scale of 0 to 10 (with 0 being absence of pain and 10 being worst possible pain)
	
Date: ____/____/____
 
Day M T W TH F S SU (please circle one)
 
Headache today Y or N (please circle one)
 
If YES:
 
Time Headache Started: _____ AM/PM
 
Time Headache Stopped: _____ AM/PM
 
Pain Level at Dose Time = _____ Scale of 0 to 10 (with 0 being absence of pain and 10 being worst possible pain)

WEEK 3	WEEK 4
Date: ____ / ____ / ____ Day M T W TH F S SU (please circle one) Headache today Y or N (please circle one) If YES: Time Headache Started: _____ AM/PM Time Headache Stopped: _____ AM/PM Pain Level at Dose Time = _____ Scale of 0 to 10 (with 0 being absence of pain and 10 being worst possible pain)	Date: ____ / ____ / ____ Day M T W TH F S SU (please circle one) Headache today Y or N (please circle one) If YES: Time Headache Started: _____ AM/PM Time Headache Stopped: _____ AM/PM Pain Level at Dose Time = _____ Scale of 0 to 10 (with 0 being absence of pain and 10 being worst possible pain)
Date: ____ / ____ / ____ Day M T W TH F S SU (please circle one) Headache today Y or N (please circle one) If YES: Time Headache Started: _____ AM/PM Time Headache Stopped: _____ AM/PM Pain Level at Dose Time = _____ Scale of 0 to 10 (with 0 being absence of pain and 10 being worst possible pain)	Date: ____ / ____ / ____ Day M T W TH F S SU (please circle one) Headache today Y or N (please circle one) If YES: Time Headache Started: _____ AM/PM Time Headache Stopped: _____ AM/PM Pain Level at Dose Time = _____ Scale of 0 to 10 (with 0 being absence of pain and 10 being worst possible pain)
Date: ____ / ____ / ____ Day M T W TH F S SU (please circle one) Headache today Y or N (please circle one) If YES: Time Headache Started: _____ AM/PM Time Headache Stopped: _____ AM/PM Pain Level at Dose Time = _____ Scale of 0 to 10 (with 0 being absence of pain and 10 being worst possible pain)	Date: ____ / ____ / ____ Day M T W TH F S SU (please circle one) Headache today Y or N (please circle one) If YES: Time Headache Started: _____ AM/PM Time Headache Stopped: _____ AM/PM Pain Level at Dose Time = _____ Scale of 0 to 10 (with 0 being absence of pain and 10 being worst possible pain)
Date: ____ / ____ / ____ Day M T W TH F S SU (please circle one)	Date: ____ / ____ / ____ Day M T W TH F S SU (please circle one)

one) Headache today Y or N (please circle one) If YES: Time Headache Started: _____ AM/PM Time Headache Stopped: _____ AM/PM Pain Level at Dose Time = _____ Scale of 0 to 10 (with 0 being absence of pain and 10 being worst possible pain)
	
one) Headache today Y or N (please circle one) If YES: Time Headache Started: _____ AM/PM Time Headache Stopped: _____ AM/PM Pain Level at Dose Time = _____ Scale of 0 to 10 (with 0 being absence of pain and 10 being worst possible pain)


Date: ____/____/ Day M T W TH F S SU (please circle one) Headache today Y or N (please circle one) If YES: Time Headache Started: _____ AM/PM Time Headache Stopped: _____ AM/PM Pain Level at Dose Time = _____ Scale of 0 to 10 (with 0 being absence of pain and 10 being worst possible pain)
	
Date: ____/____/ Day M T W TH F S SU (please circle one) Headache today Y or N (please circle one) If YES: Time Headache Started: _____ AM/PM Time Headache Stopped: _____ AM/PM Pain Level at Dose Time = _____ Scale of 0 to 10 (with 0 being absence of pain and 10 being worst possible pain)

Date: ____/____/ Day M T W TH F S SU (please circle one) Headache today Y or N (please circle one) If YES: Time Headache Started: _____ AM/PM Time Headache Stopped: _____ AM/PM Pain Level at Dose Time = _____ Scale of 0 to 10 (with 0 being absence of pain and 10 being worst possible pain)
	
Date: ____/____/ Day M T W TH F S SU (please circle one) Headache today Y or N (please circle one) If YES: Time Headache Started: _____ AM/PM Time Headache Stopped: _____ AM/PM Pain Level at Dose Time = _____ Scale of 0 to 10 (with 0 being absence of pain and 10 being worst possible pain)

Date: ____/____/ Day M T W TH F S SU (please circle one) Headache today Y or N (please circle one) If YES:
	
Date: ____/____/ Day M T W TH F S SU (please circle one) Headache today Y or N (please circle one) If YES:

Time Headache Started: _____ AM/PM	Time Headache Started: _____ AM/PM
Time Headache Stopped: _____ AM/PM	Time Headache Stopped: _____ AM/PM
Pain Level at Dose Time = _____ Scale of 0 to 10 (with 0 being absence of pain and 10 being worst possible pain)	Pain Level at Dose Time = _____ Scale of 0 to 10 (with 0 being absence of pain and 10 being worst possible pain)

WEEK 5	WEEK 6

Date: ____ / ____ / ____ Day M T W TH F S SU (please circle one) Headache today Y or N (please circle one) If YES: Time Headache Started: _____ AM/PM Time Headache Stopped: _____ AM/PM Pain Level at Dose Time = _____ Scale of 0 to 10 (with 0 being absence of pain and 10 being worst possible pain)
	
Date: ____ / ____ / ____ Day M T W TH F S SU (please circle one) Headache today Y or N (please circle one) If YES: Time Headache Started: _____ AM/PM Time Headache Stopped: _____ AM/PM Pain Level at Dose Time = _____ Scale of 0 to 10 (with 0 being absence of pain and 10 being worst possible pain)


Date: ____ / ____ / ____ Day M T W TH F S SU (please circle one) Headache today Y or N (please circle one) If YES: Time Headache Started: _____ AM/PM Time Headache Stopped: _____ AM/PM Pain Level at Dose Time = _____ Scale of 0 to 10 (with 0 being absence of pain and 10 being worst possible pain)
	
Date: ____ / ____ / ____ Day M T W TH F S SU (please circle one) Headache today Y or N (please circle one) If YES: Time Headache Started: _____ AM/PM Time Headache Stopped: _____ AM/PM Pain Level at Dose Time = _____ Scale of 0 to 10 (with 0 being absence of pain and 10 being worst possible pain)

Date: ____ / ____ / ____ Day M T W TH F S SU (please circle one) Headache today Y or N (please circle one) If YES: Time Headache Started: _____ AM/PM Time Headache Stopped: _____ AM/PM Pain Level at Dose Time = _____ Scale of 0 to 10 (with 0 being absence of pain and 10 being worst possible pain)
	
Date: ____ / ____ / ____ Day M T W TH F S SU (please circle one) Headache today Y or N (please circle one) If YES: Time Headache Started: _____ AM/PM Time Headache Stopped: _____ AM/PM Pain Level at Dose Time = _____ Scale of 0 to 10 (with 0 being absence of pain and 10 being worst possible pain)

Date: ____ / ____ / ____ Day M T W TH F S SU (please circle one)
	
Date: ____ / ____ / ____ Day M T W TH F S SU (please circle one)

one) Headache today Y or N (please circle one) If YES: Time Headache Started: _____ AM/PM Time Headache Stopped: _____ AM/PM Pain Level at Dose Time = _____ Scale of 0 to 10 (with 0 being absence of pain and 10 being worst possible pain)
	
one) Headache today Y or N (please circle one) If YES: Time Headache Started: _____ AM/PM Time Headache Stopped: _____ AM/PM Pain Level at Dose Time = _____ Scale of 0 to 10 (with 0 being absence of pain and 10 being worst possible pain)

Date: ____/____/ Day M T W TH F S SU (please circle one) Headache today Y or N (please circle one) If YES: Time Headache Started: _____ AM/PM Time Headache Stopped: _____ AM/PM Pain Level at Dose Time = _____ Scale of 0 to 10 (with 0 being absence of pain and 10 being worst possible pain)
	
Date: ____/____/ Day M T W TH F S SU (please circle one) Headache today Y or N (please circle one) If YES: Time Headache Started: _____ AM/PM Time Headache Stopped: _____ AM/PM Pain Level at Dose Time = _____ Scale of 0 to 10 (with 0 being absence of pain and 10 being worst possible pain)


Date: ____/____/ Day M T W TH F S SU (please circle one) Headache today Y or N (please circle one) If YES: Time Headache Started: _____ AM/PM Time Headache Stopped: _____ AM/PM Pain Level at Dose Time = _____ Scale of 0 to 10 (with 0 being absence of pain and 10 being worst possible pain)
	
Date: ____/____/ Day M T W TH F S SU (please circle one) Headache today Y or N (please circle one) If YES: Time Headache Started: _____ AM/PM Time Headache Stopped: _____ AM/PM Pain Level at Dose Time = _____ Scale of 0 to 10 (with 0 being absence of pain and 10 being worst possible pain)

Date: ____/____/ Day M T W TH F S SU (please circle one) Headache today Y or N (please circle one) If YES:
	
Date: ____/____/ Day M T W TH F S SU (please circle one) Headache today Y or N (please circle one) If YES:

Time Headache Started: _____ AM/PM	Time Headache Started: _____ AM/PM
Time Headache Stopped: _____ AM/PM	Time Headache Stopped: _____ AM/PM
Pain Level at Dose Time = _____ Scale of 0 to 10 (with 0 being absence of pain and 10 being worst possible pain)	Pain Level at Dose Time = _____ Scale of 0 to 10 (with 0 being absence of pain and 10 being worst possible pain)

WEEK 7	WEEK 8
Date: ____ / ____ / ____ Day M T W TH F S SU (please circle one) Headache today Y or N (please circle one) If YES: Time Headache Started: _____ AM/PM Time Headache Stopped: _____ AM/PM Pain Level at Dose Time = _____ Scale of 0 to 10 (with 0 being absence of pain and 10 being worst possible pain)	Date: ____ / ____ / ____ Day M T W TH F S SU (please circle one) Headache today Y or N (please circle one) If YES: Time Headache Started: _____ AM/PM Time Headache Stopped: _____ AM/PM Pain Level at Dose Time = _____ Scale of 0 to 10 (with 0 being absence of pain and 10 being worst possible pain)
Date: ____ / ____ / ____ Day M T W TH F S SU (please circle one) Headache today Y or N (please circle one) If YES: Time Headache Started: _____ AM/PM Time Headache Stopped: _____ AM/PM Pain Level at Dose Time = _____ Scale of 0 to 10 (with 0 being absence of pain and 10 being worst possible pain)	Date: ____ / ____ / ____ Day M T W TH F S SU (please circle one) Headache today Y or N (please circle one) If YES: Time Headache Started: _____ AM/PM Time Headache Stopped: _____ AM/PM Pain Level at Dose Time = _____ Scale of 0 to 10 (with 0 being absence of pain and 10 being worst possible pain)
Date: ____ / ____ / ____ Day M T W TH F S SU (please circle one) Headache today Y or N (please circle one) If YES: Time Headache Started: _____ AM/PM Time Headache Stopped: _____ AM/PM Pain Level at Dose Time = _____ Scale of 0 to 10 (with 0 being absence of pain and 10 being worst possible pain)	Date: ____ / ____ / ____ Day M T W TH F S SU (please circle one) Headache today Y or N (please circle one) If YES: Time Headache Started: _____ AM/PM Time Headache Stopped: _____ AM/PM Pain Level at Dose Time = _____ Scale of 0 to 10 (with 0 being absence of pain and 10 being worst possible pain)
Date: ____ / ____ / ____	Date: ____ / ____ / ____

Day M T W TH F S SU (please circle one)
 
Headache today Y or N (please circle one)
 
If YES:
 
Time Headache Started: _____ AM/PM
 
Time Headache Stopped: _____ AM/PM
 
Pain Level at Dose Time = _____ Scale of 0 to 10 (with 0 being absence of pain and 10 being worst possible pain)
	
Day M T W TH F S SU (please circle one)
 
Headache today Y or N (please circle one)
 
If YES:
 
Time Headache Started: _____ AM/PM
 
Time Headache Stopped: _____ AM/PM
 
Pain Level at Dose Time = _____ Scale of 0 to 10 (with 0 being absence of pain and 10 being worst possible pain)

Date: ____ / ____ / ____
 
Day M T W TH F S SU (please circle one)
 
Headache today Y or N (please circle one)
 
If YES:
 
Time Headache Started: _____ AM/PM
 
Time Headache Stopped: _____ AM/PM
 
Pain Level at Dose Time = _____ Scale of 0 to 10 (with 0 being absence of pain and 10 being worst possible pain)
	
Date: ____ / ____ / ____
 
Day M T W TH F S SU (please circle one)
 
Headache today Y or N (please circle one)
 
If YES:
 
Time Headache Started: _____ AM/PM
 
Time Headache Stopped: _____ AM/PM
 
Pain Level at Dose Time = _____ Scale of 0 to 10 (with 0 being absence of pain and 10 being worst possible pain)


Date: ____ / ____ / ____
 
Day M T W TH F S SU (please circle one)
 
Headache today Y or N (please circle one)
 
If YES:
 
Time Headache Started: _____ AM/PM
 
Time Headache Stopped: _____ AM/PM
 
Pain Level at Dose Time = _____ Scale of 0 to 10 (with 0 being absence of pain and 10 being worst possible pain)
	
Date: ____ / ____ / ____
 
Day M T W TH F S SU (please circle one)
 
Headache today Y or N (please circle one)
 
If YES:
 
Time Headache Started: _____ AM/PM
 
Time Headache Stopped: _____ AM/PM
 
Pain Level at Dose Time = _____ Scale of 0 to 10 (with 0 being absence of pain and 10 being worst possible pain)

Date: ____ / ____ / ____
 
Day M T W TH F S SU (please circle one)
 
Headache today Y or N (please circle one)
	
Date: ____ / ____ / ____
 
Day M T W TH F S SU (please circle one)
 
Headache today Y or N (please circle one)

If YES: Time Headache Started: _____ AM/PM Time Headache Stopped: _____ AM/PM Pain Level at Dose Time = _____ Scale of 0 to 10 (with 0 being absence of pain and 10 being worst possible pain)	If YES: Time Headache Started: _____ AM/PM Time Headache Stopped: _____ AM/PM Pain Level at Dose Time = _____ Scale of 0 to 10 (with 0 being absence of pain and 10 being worst possible pain)
---	---

